2.5.2 Statistical hypothesis, model, and method of analysis

In the primary analysis, the ARR will be estimated by a negative binomial regression model with log-link function, the cumulative number of confirmed MS relapses per subject as the response variable, number of relapses in the previous two years before enrollment and baseline EDSS as continuous covariates. Natural log of time on study in years will be used as the offset variable to account for the varying lengths of subjects' time in the study. The adjusted ARR (i.e. model-based estimate adjusted for covariates) and the corresponding 95% confidence interval will be obtained.

In case of non-convergence, continuous covariates may be removed from the regression model in the order of: baseline EDSS, number of relapses in the previous two years.

The primary analysis will only be performed for the Adult group.

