12.4.2 Statistical model, hypothesis, and method of analysis

In the primary analysis, the ARR will be estimated by a negative binomial regression model with log-link function, the cumulative number of confirmed MS relapses per participant as the response variable, number of relapses in the previous year (or two years) before enrollment, baseline EDSS and baseline number of Gd-enhancing T1 lesions at baseline as covariates. Natural log of time on study in years will be used as the offset variable to account for the varying lengths of participants' time in the study. The adjusted ARR (i.e., model-based estimate adjusted for covariates) and the corresponding 95% confidence interval will be obtained.

The primary analysis will be performed for FAS.

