12.4.4 Sensitivity and Supportive analyses

The primary analysis will be repeated based on all reported MS relapses (rather than on only the confirmed ones) for FAS population.

A summary of ARR time-based and ARR patient-based will also be given. Time-based ARRs are calculated by taking the total number of relapses observed for all participants in FAS divided by the total number of days in study of those participants and multiplied by 365.25 days. Also patient-based ARR is presented, where individual ARRs are computed and summarized over participants for FAS population. For above ARR calculations, the analysis will consider confirmed relapses only.

Additional sensitivity analyses may be defined in the analysis plan.

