2.5.4 Supportive analyses

The primary analysis will be repeated to analyze all reported MS relapses (confirmed and unconfirmed) for Adult group.

ARR time-based and ARR patient-based by age group will be provided for confirmed relapses and then for all relapses (confirmed and unconfirmed). ARRs using a “time-based approach” are calculated by taking the total number of relapses observed for all subjects within an age group divided by the total number of days in study of all subjects within the group and multiplied by 365.25 days. “Patient-based approach” is calculated in the way where individual ARRs are computed and summarized over subjects within an age group.

Listings of relapses along with their confirmation status (confirmed or unconfirmed) will be presented by age group.

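### The SAP plans the ARR only in adults or within age groups, so once a child is treated the protocol's FAS-wide primary ARR is not a planned output

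*SAP*

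**What the plan says.** **Protocol.** Section 12.4.2 states: "The primary analysis will be performed for FAS". Section 12.1 defines the FAS as everyone who consented and took at least one dose, with no age limit. Section 5.1 admits ages 18 to 65, and ages 10 to 17 above 40 kg. Section 4.1 sets no target number of children. Section 12.4.4 puts three more ARR outputs on the same set:

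- the repeat on all relapses: "The primary analysis will be repeated based on all reported MS relapses (rather than on only the confirmed ones) for FAS population"
- the time-based ARR: "Time-based ARRs are calculated by taking the total number of relapses observed for all participants in FAS"
- the patient-based ARR: "individual ARRs are computed and summarized over participants for FAS population"

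**SAP.** Section 2.5 names the FAS for the primary objective, but 2.5.2 closes with "The primary analysis will only be performed for the Adult group". Section 2.5.4 then says "The primary analysis will be repeated to analyze all reported MS relapses (confirmed and unconfirmed) for Adult group". It computes the time-based ARR from "the total number of relapses observed for all subjects within an age group", and for the patient-based ARR "individual ARRs are computed and summarized over subjects within an age group". Section 2.2.1 splits the age groups at 18 and explains that adults and children are to be assessed separately.

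**The concern.** ARR is the only primary endpoint. The objective, the eligibility criteria and the target of about 100 participants all cover both age groups, and the sample-size section makes no adult/child split. Protocol section 12 rules out hypothesis testing, so the estimate and its 95% confidence interval are the result of the trial.

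If the SAP is followed as written and even one child is treated, the report would give an adult ARR in place of the estimate the protocol names as primary. Children would enter the primary endpoint only as a crude figure for their own age group.

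**Working it through.** **1. The four ARR outputs side by side**

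| Output | Protocol 12.4.2 and 12.4.4 | SAP 2.5.2 and 2.5.4 |
|---|---|---|
| Negative binomial model, confirmed relapses | FAS | Adults only |
| Same model, all reported relapses | FAS | Adults only |
| Time-based ARR | FAS pooled | Within age group |
| Patient-based ARR | FAS pooled | Within age group |

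**2. Does other SAP text supply the total?** SAP 2.1 sets a default of all subjects in the analysis set, but only where nothing else is stated; 2.5.2 and 2.5.4 state something else. Sections 2.3.1, 2.3.3, 2.4.1 and 2.4.2 each ask for an overall summary after the age groups, and 2.5.4 does not. Naming the FAS and then fitting adults only is a convention the SAP also uses for MRI (2.7 and 2.7.2). The discrepancy is therefore with the protocol, not within the SAP.

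**3. The plan's own precision figure** (protocol 12.8.1, SAP 3.1: ARR 0.25, k = 1, n = 80)

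- Half-width = 1.96 × √((0.25 + 0.25²)/80) = 1.96 × 0.0625 = 0.1225.
- Range: 0.1275 to 0.3725, which rounds to the stated 0.13 to 0.37.
- Total: 80/0.80 = 100, as stated.
- The same formula with two years of follow-up per participant: 1.96 × √((0.25/2 + 0.25²)/80) = 0.0949.

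**4. How far the FAS rate can lie from the adult rate.** The documents give neither the child share c nor the child-to-adult rate ratio RR, so both are assumed. With equal follow-up, FAS ARR = 0.25 × ((1 − c) + c × RR).

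| c | RR 0.5 | RR 1 | RR 2 | RR 3 |
|---|---|---|---|---|
| 3% | 0.246 | 0.250 | 0.258 | 0.265 |
| 5% | 0.244 | 0.250 | 0.263 | 0.275 |
| 10% | 0.238 | 0.250 | 0.275 | 0.300 |

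The largest shift is 0.300 − 0.250 = 0.05. At RR 3, a shift equal to the stated half-width needs a child share of 0.12/(0.25 × 2) = 24%.

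**5. Precision lost by leaving children out.** With 5% children, n = 76 and the half-width is 0.1257. With 10%, n = 72 and it is 0.1291. With everyone included it is 0.1225.

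**6. Does the model work on the FAS without an age term?** This was simulated with 100 participants, 24 months, 20% drop-out at a uniform time, k = 1, and an intercept-only negative binomial model with log-time offset (1,500 trials per scenario). With 3, 5 or 10 children, the FAS fit averaged 0.237 to 0.299 against true FAS rates of 0.238 to 0.300, with 94% to 96% coverage. Selected scenarios:

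| Children | RR | Mean adult fit | Mean FAS fit | Adult CI contains FAS rate | FAS CI contains FAS rate |
|---|---|---|---|---|---|
| 5 | 0.5 | 0.248 | 0.242 | 95.6% | 95.8% |
| 5 | 3 | 0.252 | 0.277 | 92.5% | 94.8% |
| 10 | 0.5 | 0.250 | 0.237 | 93.8% | 94.7% |
| 10 | 2 | 0.252 | 0.277 | 92.1% | 94.7% |
| 10 | 3 | 0.250 | 0.299 | 84.6% | 95.3% |

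The 84.6% reflects a different target population; the adult interval is not faulty for adults.

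**7. Why an age term should not be required.** At equal rates, the chance that a child has no relapse is 1/(1 + 0.5) = 0.667 over two full years. Averaged over a uniform drop-out time it is ln(1.5)/0.5 = 0.811. The mix is 0.8 × 0.667 + 0.2 × 0.811 = 0.696. All children are relapse-free with probability 0.696³ ≈ 34% for 3 children and 0.696⁵ ≈ 16% for 5. An age effect could not then be estimated.

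**The case against.** **The adult restriction looks deliberate.** It is pre-specified, recurs in both MRI models, and has a stated reason in SAP 2.2.1. A pooled rate also depends on an age mix that nobody planned. This supports reporting an adult estimate. It does not explain dropping the total that the protocol names as primary, because showing ages separately does not require omitting the whole.

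**SAP section 4, on changes to protocol-specified analyses, is blacked out.** The change may be declared there, so nothing here says it is undeclared; the statement concerns the visible text only. A declaration would still leave the FAS model estimate without a planned output.

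**The missing overall row may be loose wording.** SAP 2.3.3 opens with age group alone and adds the overall summary a sentence later, and unseen table shells may include a total. This has some force for the crude ARRs, but 2.5.4 has no such follow-up sentence and its formulas are written within group. It has no force for the two models, which are explicitly adult.

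**The effect is small.** This stands. The pooled crude ARR matched the intercept-only FAS fit to three decimals in every simulated scenario, and a time-based total could be rebuilt by hand from group totals. The covariate-adjusted FAS estimate and its interval could not.

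**The simulation has no covariates.** This also stands: its coverage figures are indicative and do not describe the adjusted model.

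**Conclusion.** The concern holds and should be fixed. The SAP's primary analysis population is not the protocol's, and if any child is treated the visible SAP plans no FAS-wide ARR, model-based or crude.

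The effect is zero if no child is treated, because the adult group is then the FAS. Otherwise it rests on the assumed child share and rate ratio. Over the ranges examined the shift is at most 0.05, against half-widths of 0.12 (as planned) and 0.095 (two years of follow-up). What is lost is a protocol-defined primary estimate; no decision threshold is affected.

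Two side points carry no weight in this conclusion. SAP 2.5.2 omits the baseline count of Gd-enhancing T1 lesions that protocol 12.4.2 lists as a covariate. It also does not say whether the adjusted ARR is taken at covariate means or averaged over participants.

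**What to change.** - **SAP 2.5.2:** replace the closing sentence so that the primary model is fitted on the FAS, in line with protocol 12.4.2, with the same model also fitted in adults. Do not require an age-group term.
- **SAP 2.5.4:** run the all-reported-relapses repeat on the FAS beside the adult fit, and add an overall row to the time-based and patient-based ARRs.
- **If adults are to be the headline:** state this as a change from the protocol and still report the FAS model.
- **Minor:** restore the Gd-enhancing lesion covariate or state its removal as a change, and add one sentence on how the adjusted ARR is evaluated.

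The cost is SAP wording, one more run of each of two existing models and one more table row, with no new data. The downside is that the FAS and adult ARRs must be clearly labelled so that they are not confused.

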2.5.3 Handling of missing values/censoring/discontinuations

According to the protocol, subjects who discontinue study treatment should remain in the study and follow the assessment schedule. The primary analysis will use all available data up to the end of treatment period date, irrespective of on or off study treatment.

For subjects who early withdraw from the study, the number of relapses up to the study discontinuation will be used for the primary analysis. No imputation will be applied to the incomplete study duration.

The primary negative binomial regression model with an offset for the time in study adjusts for missing information (drop-out) under the assumption of non-informative drop-out, information is missing at random, and constant relapse rate over time.

2.5.4 Supportive analyses

The primary analysis will be repeated to analyze all reported MS relapses (confirmed and unconfirmed) for Adult group.

ARR time-based and ARR patient-based by age group will be provided for confirmed relapses and then for all relapses (confirmed and unconfirmed). ARRs using a “time-based approach” are calculated by taking the total number of relapses observed for all subjects within an age group divided by the total number of days in study of all subjects within the group and multiplied by 365.25 days. “Patient-based approach” is calculated in the way where individual ARRs are computed and summarized over subjects within an age group.

Listings of relapses along with their confirmation status (confirmed or unconfirmed) will be presented by age group.

2.6 Analysis of the key secondary objective

Not applicable as there is no key secondary objective in this study.

2.7 Analysis of secondary efficacy objective(s)

All analyses for secondary efficacy objectives will be conducted using the FAS.

For MRI parameters, only assessments taken within 30 days from the last dose date will be included in the analysis.

2.7.1 Secondary endpoints

Secondary efficacy endpoints include:

- To estimate annualized rate of new or newly enlarged T2 lesions, below variables will be derived:
 - The total number of new or newly enlarged T2 lesions within 30 days from the last dose date will be derived by taking the sum of number of new or newly enlarged T2 lesions from all scheduled MRI scans (as compared to the previous scan) with a non-missing value within 30 days from the last dose date.
 - The time (in years) from screening scan will be calculated as (date of last scheduled MRI scan with a non-missing value for the number of new or enlarging T2 lesions within 30 days from the last dose date – date of screening scan +1)/365.25.
- Volume of T2 lesions.
- To estimate the number of Gd-enhancing T1 lesions per scan, below variables will be derived:
 - The total number of Gd-enhancing T1 lesions within 30 days from the last dose date will be derived by taking the sum of number of Gd-enhancing T1 lesions from the all scheduled MRI scan with a non-missing value within 30 days from the last dose date. Any Gd-enhanced T1 data obtained less than 30 days after the termination of steroid therapy which is used to treat MS relapses will not be included in analysis of Gd-enhancing T1 lesion related endpoint.
 - The number of MRI scans will be derived by counting the number of scheduled MRI scans with non-missing values for the number of Gd-enhancing T1 lesions within 30 days from the last dose date (i.e. the number of scans contributed to the derivation of the above variable: the total number of Gd-enhancing T1 lesions within 30 days from the last dose date).
- Volume of Gd-enhancing T1 lesions.
- Number of T1 hypo-intense lesions.
- Volume of T1 hypo-intense lesions.

Change and % change in volume of T2 lesions, Gd-enhancing T1 lesions and T1 hypo-intense lesions from baseline will only be defined for subjects with both baseline and post-baseline values and will be calculated as:

change from baseline = post-baseline value – baseline value;

% change from baseline = change from baseline / baseline value*100.

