8.3.2 Efficacy assessment 2

Expanded Disability Status Scale (EDSS).

The EDSS is an ordinal scale used for assessing neurologic impairment in MS based on a neurological examination. It consists of scores in each of seven functional systems (FSs) that are then combined to determine the EDSS steps [ranging from 0 (normal) to 10 (death due to MS)]. The FSs are Visual, Brain Stem, Pyramidal, Cerebellar, Sensory, Bowel & Bladder, and Cerebral functions. The FSs and EDSS steps will be assessed in a standardized manner. EDSS is a widely used and accepted instrument to evaluate disability status at a given time and, longitudinally, to assess disability progression in clinical studies in MS.

[REDACTED] EDSS assessments obtained on an unscheduled visit can only be used to mark the onset of a possible sustained progression.

Patient who dies due to MS will be counted as progression. A patient who misses one or more scheduled visits that are preceded [REDACTED]

MRI parameters: T1 hypo-intense lesion number and volume; T2 lesion volume, new/newly enlarged T2 lesion number; Gd- enhancing T1 lesion number and volume;

All participants will undergo MRI scanning of the brain in accordance with the study Imaging Acquisition Guidelines during the Screening visit (up to 30 days prior to day 1), provided the participant meets all other I/E criteria, and then for the Month 12 and Month 24 visits. Each MRI scan performed for the study needs to be centrally reviewed by a neuro-radiologist from the sponsor designated imaging vendor as part of the efficacy analysis. Each site investigator will be responsible to have a qualified neuro-radiologist review each MRI scan to determine if there may be any incidental findings unrelated to the planned observations within the study protocol detected on the images. Refer to [Section 16.7](#) Appendix 7 for Guidance on Safety monitoring.

Participant suspected MS relapse could undergo additional MRI scan on his/her own account in alignment with the investigator. To avoid potential interference caused by steroids used for the treatment of MS relapses, the following restrictions will be applied for this study:

- In case of relapse, if an MRI would have been scheduled within 30 days of the initiation of steroid treatment, this MRI should be performed before steroid treatment is initiated.
- No MRI scan should be performed while a participant is on intravenous steroid therapy and within 30 days after termination of steroid therapy.

Scanning

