2.7.2 Statistical hypothesis, model, and method of analysis

Methods of analyses for efficacy endpoints defined in [Section 2.7.1](#) are described below.

- The annualized rate of new or newly enlarged T2 lesions for Adult group will be estimated by a negative binomial regression model with log-link function, the total number of new or newly enlarged T2 lesions within 30 days from the last dose date (per subject) as the response variable. Natural log of time from screening scan in years will be used as the offset. The model will include baseline age and baseline volume of T2 lesions as continuous covariates. The estimated number of new or newly enlarged T2 lesions will be obtained together with the corresponding 95% confidence interval.

Supportive analyses: similar analyses may also be conducted to obtain the estimated annualized rate of new or newly enlarged T2 lesions at month 0 to month 12 and at month 12 to month 24 for Adult group.

Descriptive summary statistics (mean, median, standard deviation, min, max) for the number of new or newly enlarged T2 lesions will be provided by age group and by visit. Number and percentage of subjects free of new or newly enlarged T2 lesions will also be provided by age group.

- The number of Gd-enhancing T1 lesions per scan for Adult group will be estimated by a negative binomial regression model with log-link function, the total number of Gd-enhancing T1 lesions within 30 days from the last dose date (per subject) as the response variable. Natural log of the number of MRI scans will be used as the offset. The model will include baseline age and number of Gd-enhancing T1 lesions at baseline as continuous covariates. The estimated number of Gd-enhancing T1 lesions per scan will be obtained together with the corresponding 95% confidence interval.

Supportive analyses: descriptive summary statistics (mean, median, standard deviation, min, max) for the number of Gd-enhancing T1 lesions will be provided by age group and by visit. Number and percentage of subjects free of Gd-enhancing T1 lesions will also be provided by age group.

- Descriptive summary statistics (mean, median, standard deviation, min, max) will be provided by age group and by visit for the following: volume of T2 lesions, volume of Gd-enhancing T1 lesions, number of T1 hypo-intense lesions, volume of T1 hypo-intense lesions, change and % change in volume of T2 lesions, Gd-enhancing T1 lesions and T1 hypo-intense lesions from baseline.

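### The T2 lesion rate keeps the time of an earlier interval whose count is missing, so the annualized rate is understated for that participant

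*SAP*

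**What the plan says.** SAP 2.7.1 derives two variables for the T2 rate.

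- **Count.** The total is obtained "by taking the sum of number of new or newly enlarged T2 lesions from all scheduled MRI scans (as compared to the previous scan"), restricted to scans "with a non-missing value within 30 days from the last dose date".
- **Time.** The clock stops at the "date of last scheduled MRI scan with a non-missing value for the number of new or enlarging T2 lesions", under the same 30-day limit. From that date the SAP subtracts the "date of screening scan +1)/365.25".

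In SAP 2.7.2 the annualized rate in adults "will be estimated by a negative binomial regression model with log-link function, the total number of new or newly enlarged T2 lesions" being the response, and "Natural log of time from screening scan in years will be used as the offset". Baseline age and baseline T2 volume are covariates. SAP 2.7.3 adds only that missing secondary-endpoint data are not imputed.

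For Gd-enhancing lesions, SAP 2.7.1 ties the denominator to the numerator: it is "the number of scans contributed to the derivation of the above variable".

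Protocol 8.3.2 schedules MRI at Screening, Month 12 and Month 24, and Table 8-1 also marks EOT and EOS. The same section adds: "Participant suspected MS relapse could undergo additional MRI scan". Neither document says whether the previous scan means the previous scheduled scan, the previous evaluable scan or any scan.

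**The concern.** A rate is unbiased when lesions and time come from the same intervals. Here the count is built interval by interval, while the time is one span from screening to the last counted scan. The two agree only if every interval inside that span was counted.

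They disagree when an earlier comparison yields no count but a later scan is compared with a scan after screening. The typical pattern is a Month 12 scan with no count against screening that still serves as the reference for Month 24. One year of lesions is then divided by two years of time. No other SAP rule removes the uncounted year.

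The error goes one way, towards a lower lesion rate, which flatters the drug. In a single-arm study there is no control arm in which the same error would cancel.

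**Working it through.** The documents state no value for the T2 rate, so there is no plan figure to reproduce.

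**Inputs from the documents.** Screening scan up to 30 days before Day 1 (Protocol 8.3.2); Month 12 = day 360 and Month 24 = day 720 (SAP Table 2-3); no day 0 (SAP Table 2-1); one day added to the time (SAP 2.7.1).

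**Assumptions.** The share *f* of participants with an uncounted first interval, and the course of the lesion rate over time.

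**Step 1: one participant, constant true rate.** With the screening scan on day −30, the SAP time to Month 24 is 720 + 30 − 1 + 1 = 750 days (2.053 years). With day −1 it is 721 days (1.974 years). Month 12 to Month 24 is 360 days. The ratio of the SAP rate to the true rate is days counted divided by SAP days.

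| Pattern | Screening day −30 | Screening day −1 |
|---|---|---|
| Both counts present | 749/750 = 0.999 | 720/721 = 0.999 |
| Month 24 count missing | 389/390 = 0.997 | 360/361 = 0.997 |
| Month 12 scan absent, Month 24 read against screening | 749/750 = 0.999 | 720/721 = 0.999 |
| Month 12 count missing, Month 24 read against Month 12 | 360/750 = 0.480 | 360/721 = 0.499 |

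Only the last row is biased. The added day costs less than 0.3%. With an offset limited to the counted interval, the last row becomes 360/360 = 1.

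If year 1 has twice the rate of year 2 (say 4 and 2 lesions), the true two-year rate is 6/2 = 3 per year. The SAP gives 2/2 = 1, a loss of two thirds.

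**Step 2: the group.** Take two one-year intervals and divide the expected total count by total time.

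- Constant rate λ: [(1 − f)·2λ + f·λ]/2 = λ(1 − f/2). For f = 5% and 10% this is 0.975 and 0.95 of the true rate.
- Year 1 twice year 2 (2λ, then λ; true mean 1.5λ): [(1 − f)·3λ + f·λ]/2 = 1.5λ(1 − 2f/3). For f = 5% and 10% this is 0.967 and 0.933, or −3.3% and −6.7%.

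**Step 3: simulation.** Intercept-only negative binomial fits (80 participants, 400 runs; assumed rate and dispersion 1 and 1, or 3 and 2) at a constant rate gave 0.97, 0.95, 0.89–0.90 and 0.84–0.86 of the true rate for f = 5%, 10%, 20% and 30%. The matched offset gave 0.985 to 1.009. A second simulation (90 participants, 2,000 runs, dispersion 1.5) gave −2.5% and −5.1% at a constant rate of 2 per year, and −3.3% and −6.7% for 4 then 2 per year, at f = 5% and 10%.

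**Step 4: what the matched offset leaves.** With a falling rate, affected participants contribute only the quieter year. The pooled ratio to λ is (3 − 2f)/(2 − f). For f = 5%, 2.9/1.95 = 1.487 against 1.5 (−0.9%); for f = 10%, 2.8/1.9 = 1.474 (−1.8%). The second simulation gave −0.8% and −1.7%.

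**Step 5: set against sampling error.** With a mean of 4 lesions over two years, dispersion 1.5 and 90 adults, the standard error of the log rate is √((1/4 + 1.5)/90) = 0.139. The 95% interval then runs from about −24% to +31% around the estimate.

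**The case against.** **The pattern is narrow.** The offset stops at the last counted scan, so a missing final count, as with dropout, is handled correctly. A Month 12 scan that was never done is also harmless if Month 24 is read against screening. The 30-day limit applies to count and time alike. The steroid exclusion in SAP 2.7.1 concerns Gd data only. If the screening scan gives no T2 volume, the baseline covariate is missing and the participant probably leaves the model. What remains is a screening scan good enough for volume but not for comparison, or a Month 12 scan used as reference yet given no count. Central review, phantom scans and fixed acquisition settings (Protocol 8.3.2) should keep both uncommon. All of this stands and limits the frequency. It does not supply the missing rule.

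**The size is assumed and small.** The 5% and 10% shares are not in the documents, and a bias of a few percent lies well inside the sampling error in step 5. The endpoint is secondary, and Protocol section 12 rules out hypothesis testing. SAP 2.7.2 also plans T2 counts by visit and allows separate rates for each year, which could expose a gap. This stands too, though the yearly rates are optional.

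**The Gd comparison is imperfect.** A per-scan count naturally has scans as its denominator. True, but the principle of matching denominator to numerator carries over to time.

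**Stronger readings that the documents do not support.** A reader might infer that the rate is divided by all time since screening, so that every dropout dilutes it; the stated end of the clock rules this out. A reader might also infer that extra scans at suspected relapse become the reference and hide lesions in the most active participants. That needs those scans to reach the central reader, which is not stated: they are at the participant's own expense, and central review is required for scans performed for the study. SAP 2.1.2.1 leaves unscheduled visits out of efficacy visit mapping, and the previous scheduled scan is the more natural reading. Nothing in the documents shows that participants with suspected relapse carry most of the lesion activity.

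**Conclusion.** The mismatch is real but confined to an uncounted earlier interval followed by a scan read against a scan after screening. In that pattern the participant's rate is 0.48 to 0.50 of the true value at a constant rate, and one third of it if year 1 has twice the rate of year 2.

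The group effect rests on an assumed share of affected participants: about 2.5% or 5% too low at a constant rate for shares of 5% or 10%, and about 3.3% or 6.7% too low with the falling rate. The direction is always downward. Imaging vendor documents that cannot be seen here may already fix the reference scan; the SAP itself does not. This is a worthwhile tidying of a stated formula and does not threaten the study's conclusions.

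**What to change.** Make two changes in SAP 2.7.1.

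1. Define the offset as the sum, over the scans whose count enters the numerator, of the time from the reference scan used for that count to the scan itself. Only counted intervals then contribute time.
2. State that the previous scan means the previous scheduled scan with an evaluable T2 reading.

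The cost is two sentences and a small programming change that needs the reference scan date for each count. No new assessments are needed. Apart from how the added day is treated, results do not change for participants with complete scheduled counts and no extra scan. A small downward bias remains if the lesion rate falls over time (step 4).

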6.2 Other treatment(s)

6.2.1 Concomitant therapy

All drug used in previous MS disease modifying treatment should be captured on the "Previous MS disease modifying Treatment" eCRF.

All other concomitant medications taken within 30 days prior to Screening and during the study the respective information needs to be recorded in the eCRF. The investigator should instruct

the participant to notify the study site about any new medications he/she takes after the start of the study drug. Both the start date and the end date, for each medication should be captured on the Concomitant Medication CRF.

Use of the following treatments are recommended to manage potential adverse reactions associated with the study drug:

- anticholinergics (atropine s.c. or i.v.) for treatment of symptomatic bradycardia as the first line treatment, up to 3 mg/day;
- beta-agonists/sympathomimetics (dopamine drip 5-20 µg/kg/min or epinephrine drip 2-10 µg/min) for treatment of non-responsive bradycardia.

For more recommendations for management of bradycardia, refer to [Section 16.5](#).

A short course of intravascular corticosteroids (methylprednisolone) is allowed for the treatment of MS relapses.

The medications allowed for treatment of adverse reactions and MS relapses are not considered study supplies, and therefore, need to be supplied by the study site or only 0.5mg fingolimod will be supplied by sponsor.

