2.7.3 Handling of missing values/censoring/discontinuations

As a general rule, missing data will not be imputed in any secondary endpoint analyses. For MRI parameters, only assessments taken within 30 days from the last dose date will be included in the analysis.

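### The SAP drops Gd-enhancing T1 data from the 30 days after relapse steroids but has no rule for scans taken during the course, which the protocol also bars

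*SAP*

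**What the plan says.** Protocol 8.3.2 gives the reason for its scan restrictions: "To avoid potential interference caused by steroids used for the treatment of MS relapses, the following restrictions will be applied for this study". One restriction asks that an MRI falling due within 30 days of starting steroids be done before they start. The other is: "No MRI scan should be performed while a participant is on intravenous steroid therapy and within 30 days after termination of steroid therapy". It names two barred periods, the course itself and the 30 days after it.

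SAP 2.7.1 forms the Gd-enhancing T1 total from every eligible scheduled scan, with the time limit set relative to the final dose: "taking the sum of number of Gd-enhancing T1 lesions from the all scheduled MRI scan with a non-missing value within 30 days from the last". It then sets one steroid exclusion, which applies to the following: "Any Gd-enhanced T1 data obtained less than 30 days after the termination of steroid therapy which is used to treat MS relapses". The stated consequence is that such data "will not be included in analysis of Gd-enhancing T1 lesion related endpoint". The scan count used as the offset is defined as the scans that contributed to that total.

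The only other restriction on MRI data is in SAP 2.7 and 2.7.3, and it concerns the last dose, not steroids: "For MRI parameters, only assessments taken within 30 days from the last dose date will be included in the analysis". SAP 2.7.2 adds no steroid rule.

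Steroids for relapse are permitted under Protocol 6.2.1: "A short course of intravascular corticosteroids (methylprednisolone) is allowed for the treatment of MS relapses". No course length is given.

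**The concern.** The SAP exclusion exists to handle scans taken when the protocol says they should not be. The protocol sentence behind it covers two periods, and the SAP covers one. As worded, a scheduled scan in the middle of a steroid course contributes to both the Gd lesion total and the scan count, while a scan 29 days after the last steroid dose contributes to neither. That cannot be the intended ordering if the purpose is to keep steroid interference out of the endpoint.

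At stake is the estimated number of Gd-enhancing T1 lesions per scan, and the related Gd summaries, in participants treated for a relapse near a scheduled scan. There is also a smaller mismatch at the end of the window: the protocol's period includes day 30, and the SAP's stops short of it.

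**Working it through.** The plan gives no figure on this point, so there is none to reproduce. The check has two parts.

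**1. The two rules day by day.** Take an example course with first administration on day 0 and last on day 4 (five days, assumed). The SAP rule is read as 0 ≤ scan day − 4 < 30.

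| Scan day | Protocol 8.3.2 | SAP 2.7.1 |
|---|---|---|
| −1 | allowed | kept |
| 0, before first administration | allowed | kept |
| 0, after first administration | barred | **kept** |
| 1 to 3 | barred | **kept** |
| 4 (termination) to 33 | barred | dropped |
| 34 (30 days after termination) | barred | **kept** |
| 35 onward | allowed | kept |

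The rules disagree during the course and on the single day 34.

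**2. How many scans could be involved.** Inputs:

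- N = 80 to 100 participants (Protocol 12.8.1, SAP 3.1).
- Two scheduled post-baseline scans per participant, since Protocol 8.3.2 sets MRI at screening "and then for the Month 12 and Month 24 visits". This gives 2 × 80 = 160 to 2 × 100 = 200 scans.
- ARR 0.20 to 0.38 (Protocol 12.8.1, SAP 3.1).
- Course length L: not in the documents. Assumed 3 to 5 days, with 14 days as a long case.
- Further assumptions: every relapse is treated with steroids, scan timing is independent of relapse, and sites ignore the ban.

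Expected scans in a window of L days = N × 2 × ARR × L / 365.25.

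- Mid-course, lowest: 80 × 2 × 0.20 × 3 / 365.25 = 0.26.
- Mid-course, highest for a short course: 100 × 2 × 0.38 × 5 / 365.25 = 1.04.
- Mid-course, 14 days: 80 × 2 × 0.20 × 14 / 365.25 = 1.23, up to 100 × 2 × 0.38 × 14 / 365.25 = 2.91.
- The 30-day window that the SAP does cover: 80 × 2 × 0.20 × 30 / 365.25 = 2.63, up to 100 × 2 × 0.38 × 30 / 365.25 = 6.24.

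The omitted period is therefore worth about 0.3 to 1.0 scans for a short course, against about 2.6 to 6.2 in the period covered. Any compliance with the ban lowers both. Extra scans for a suspected relapse, which Protocol 8.3.2 permits, are not scheduled scans and do not enter the Gd total.

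**The case against.** The strongest reply is that a mid-course scan is already prohibited, so the SAP need not provide for it, and with the ban respected the expected number is near zero. The second half stands and limits the size of the point. The first half does not: scans within 30 days after steroids are barred by the same protocol sentence, yet the SAP excludes them explicitly.

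It can also be said that a site instruction and an analysis rule need not match to the day. That is fair for day 30, which is a tidying matter only.

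A reader might infer more than the documents support:

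- *That the rule also drops every earlier scan, including screening.* This would need the rule to be coded as scan date minus steroid end date below 30 with no lower limit. The SAP says data obtained after termination, so such coding would contradict the text.
- *That the lesion count is biased downward.* Protocol 8.3.2 speaks only of potential interference and gives no direction.
- *That 9% to 14% of something is lost.* For a 3- or 5-day course, 3/(3+30) = 9% and 5/(5+30) = 14% are shares of a calendar window of assumed length. They are not shares of scans or lesions, and they do not measure bias.
- *That end-of-treatment scans are especially exposed.* Table 8-1 marks MRI at that visit, but nothing shows that these scans cluster around steroid courses.
- *That volume and the scan-count offset escape the exclusion.* SAP 2.7.1 applies it to Gd-related endpoints generally and ties the scan count to the scans used.

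**Conclusion.** The gap is real and minor. SAP 2.7.1 omits one of the two periods barred by Protocol 8.3.2, so a scheduled scan taken mid-course would be analysed under the rule as written. The expected number is about 0 to 1 of 160 to 200 post-baseline scans for a 3- to 5-day course, and about 1.2 to 2.9 if courses lasted 14 days. These figures rest on assumed course lengths, every relapse being treated, scan timing unrelated to relapse, and no adherence to the ban. They count the whole planned sample; the Gd model is fitted in adults only, so its share can only be equal or smaller.

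The endpoint is secondary, and Protocol section 12 plans no hypothesis testing. The documents do not show that any such scan exists or which way it would move the estimate. SAP section 4, on changes to protocol-specified analyses, is redacted, so any explanation there could not be checked.

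**What to change.** Reword the sentence in SAP 2.7.1 so that Gd-enhancing T1 data are excluded when obtained during steroid therapy for an MS relapse, meaning after the first administration, or within 30 days after its termination, day 30 included. State that a scan done before the first administration is kept, even on the same date. A cut that simply starts on the steroid start date would delete the pre-steroid scan that Protocol 8.3.2 asks for.

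Two details should be settled in the same edit:

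- *Same-day scans.* Protocol 6.2.1 mentions start and end dates of medications, not times. Treat a scan dated on the start date as pre-steroid unless site records show otherwise.
- *Route.* The protocol's ban during the course names intravenous steroids, while the SAP sentence covers any relapse steroid therapy. Say which applies.

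No change is needed to carry the exclusion to Gd volume or the scan-count offset. The cost is one SAP sentence and a small programming change before database lock, using dates already collected, plus a site query for any scan dated on a steroid start date.
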